### 7.3.3 Exclusion Criteria

Patients will be excluded from the study if one or more of the following criteria are applicable:

1. Established or suspected fibrosing colonopathy
2. Total or partial gastrectomy
3. A history of solid organ transplant, or significant surgical resection of the bowel; significant resection of the bowel is defined as any resection of the terminal ileum or ileocecal valve. Patients who have had qualitative, long-term changes in nutritional status after any other bowel resection (e.g., increased or new need for pancreatic enzyme supplementation compared with preoperative status to maintain the same nutritional status) should also be excluded.
4. Any chronic diarrheal illness unrelated to pancreatic insufficiency (e.g., infectious gastroenteritis, sprue, inflammatory bowel disease)
5. Known hypersensitivity or other severe reaction to any ingredient of the investigational medicinal product (IMP)
6. Alanine aminotransferase (ALT) or aspartate aminotransferase (AST) level  $\geq 5 \times \text{ULN}$  or total bilirubin level  $\geq 1.5 \times \text{ULN}$  at the Screening visit, unless due to Gilbert's syndrome. Cases of suspected or confirmed Gilbert's syndrome should be discussed with the Medical Monitor.

7. Signs and/or symptoms of liver cirrhosis or portal hypertension (e.g., splenomegaly, ascites, esophageal varices), or documented liver disease unrelated to CF
8. Patients with a known allergy to the stool marker (FD&C Blue #2)
9. Feeding via an enteral tube during 6 months before screening
10. Routine use of anti-diarrheals, anti-spasmodics, or cathartic laxatives, or a change in chronic osmotic laxatives (e.g., polyethylene glycol) regimen in the previous 3 months prior to screening
11. History of severe constipation with <1 evacuation/week under appropriate laxative therapy within the last 12 months before screening
12. Documentation of distal intestinal pseudo-obstruction syndrome within the last 12 months before screening
13. Forced expiratory volume  $\leq 30\%$  at the screening visit
14. Lactation or known pregnancy or positive pregnancy test at screening for women of childbearing potential
15. Participation in another clinical study involving an investigational product within 30 days prior to screening.
16. Patient's with poorly controlled diabetes according to the Investigator's judgment
17. Changes in CFTR modulator therapy during the 3 months prior to screening for the trial (for patients already on CFTR modulator therapy)
18. Any condition that the Investigator believes would interfere with the intent of this study or would make participation not in the best interests of the patient.

#### **7.3.4 Removal of Patients from the Study**

A patient may be withdrawn from the study at any time for any of the following reasons:

- Lost to follow-up
- Withdrawal of consent, for any reason, at any time
- Major protocol deviations that could compromise the interpretation of the results
- Occurrence of an immunoallergic reaction
- Occurrence of an adverse reaction (i.e., an SAE related to IMP) that justifies the discontinuation of the IMP
- Pregnancy

The date of withdrawal and the reason for withdrawal must be fully documented in the case report form (CRF) and a short narrative description should be added in the patient's medical records.

If at the time of withdrawal, the patient has received the investigational study product (partially or totally), study staff should encourage the patient to attend the Early Withdrawal Visit for follow-up safety investigations. These patients will be included in the mITT efficacy analysis and safety analysis.

If the reason for discontinuation is an AE, then the Investigator will seek to obtain follow-up information and to document the event until its resolution or stabilization. In any case, the Investigator will take all necessary measures to ensure the patient's safety and ensure the patient is treated in accordance with local standard of care.

If a patient is lost to follow-up, then the Investigator should make every effort to obtain maximum information on the reasons for the nonattendance to the visit and on the patient's state of health. All attempts will be documented in the patient's medical records.

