### **8.3.3.1 Instructions for Supervised Confinement for V6 and V9**

Dosing must have occurred for at least 16 days prior to the supervised confinements. Beginning at breakfast (the first meal) on Day 1 of the supervised confinement, patients will be placed on a 72-hour controlled diet, with 100 g fat/day (3 meals and 2 snacks per day) and a minimum of 1.5 to 2 g of protein per kg of body weight. Although it is preferred to have the patient consume exactly 100 g of fat per day, the fat excretion assay remains valid with a fat intake range within 15% of the goal (i.e., 85 to 115 g of fat per day). The nutritional planning and calculation of dietary fat and nitrogen (protein) intake will be conducted by a qualified dietician at each site. The actual fat and nitrogen (protein) intake will be calculated from the recorded type and amount of food consumed. A central laboratory will calculate CFA, CNA, and stool weight values on the basis of dietary intake and the fat and nitrogen excreted in stool.

An indicator marker (500 mg of Food, Drug, and Cosmetics [FD&C] Blue #2) will be provided as two 250-mg capsules. The first marker (consisting of two 250-mg capsules) will be given at the beginning of breakfast or first meal on Day 1 of the supervised confinement to mark the start of the controlled diet. The second marker (two 250-mg capsules) will be given at the beginning of breakfast or first meal on Day 4 to mark the end of the controlled diet. Stool collection for fecal fat and nitrogen assessments must begin after the first marker has passed (the first stool containing the first marker is discarded) and is completed when the second marker has passed (the first stool containing the second marker is collected). Patients must continue the supervised confinement until the second stool marker is passed. The controlled diet will be maintained until the patient takes the second marker. Although it is not part of the controlled diet, the breakfast or first meal consumed on Day 4 of the supervised confinement should mimic (as closely as possible) the breakfast or first meal consumed on Day 1 of the supervised confinement.

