### 10.3 Analysis Sets

- Safety Set: patients receiving at least one dose of treatment. Patients will be analyzed according to the treatment actually received. The Safety Set will be used for all analyses of safety endpoints unless specified otherwise and for the summaries of patients in listings related to dosing of study drug.
- Efficacy sets:
  - mITT Set: All randomized patients receiving at least one dose of treatment and have at least one valid stool collection and CFA post baseline while receiving their assigned study drug. The mITT set is considered as the primary set for the efficacy analysis. The mITT set will be used for all analyses of efficacy endpoints.
  - Per Protocol Set: Subset of the mITT set comprising all patients who do not violate the terms of the protocol in a way that would affect the study outcome significantly, as determined by the study clinician. Protocol deviations will be captured throughout the study and classified as minor or major and reviewed at a data review meeting before database lock. Attendees will include appropriate individuals from the Sponsor and contract research organization. Each major deviation will be categorized as either important or not important with respect to the effect on the primary endpoint analysis. A sensitivity analysis will be performed in the Per Protocol Set.

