### 4.1 Modified Intent-to-Treat Population

The modified intent-to-treat (mITT) population for the crossover phase includes all randomized patients receiving at least one dose of treatment and having at least one valid stool collection and CFA post baseline while receiving their assigned study drug..

The mITT population for each stage of the extension phase includes all enrolled patients receiving at least one dose of treatment and having a valid stool collection and CFA during the relevant stage of the extension phase.

A stool sample will be considered valid if the date and time associated with the second blue dye marker is recorded, indicating that the stool sample collection is complete.

The mITT population will be used for efficacy analyses. Subjects will be analyzed according to the treatment group to which they were randomized for the crossover phase, regardless of the actual treatment received, unless stated otherwise.

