## **9. EFFICACY EVALUATION**

### **9.1 Overview of Efficacy Analysis Issues**

#### **9.1.1 Handling of Dropouts or Missing Data**

Missing data will not be replaced.

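### Protocol 7.3.4 and the mITT definition disagree on dosed patients who leave before a valid CFA, and the rule that will be applied drops these patients' malabsorption symptoms from the efficacy output

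*Protocol*

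**What the plan says.** Protocol 7.3.4 deals with patients who had received any amount of the investigational product when they withdrew. It asks sites to encourage them to attend the Early Withdrawal Visit and then states: "These patients will be included in the mITT efficacy analysis and safety analysis". It sets no CFA condition.

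Protocol 10.3, matching the synopsis, admits to the mITT set only dosed patients who "have at least one valid stool collection and CFA post baseline while receiving their assigned study drug", and adds: "The mITT set is considered as the primary set for the efficacy analysis". SAP 4.1 repeats the condition ("having at least one valid stool collection and CFA post baseline while receiving their assigned study drug") and defines validity: "A stool sample will be considered valid if the date and time associated with the second blue dye marker is recorded".

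On timing, Protocol 8.3.3.1 says of Visits 6 and 9: "Dosing must have occurred for at least 16 days prior to the supervised confinements". The Early Withdrawal Visit in Protocol 8.3.3 has no stool collection but does include an assessment of malabsorption signs and symptoms. SAP section 1 lets the SAP prevail where it differs from the protocol.

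**The concern.** A dosed patient who withdraws before completing the Visit 6 collection is in the mITT set by Protocol 7.3.4 and out of it by the other three statements. A reader of 7.3.4 would believe that such patients are counted in the efficacy results; under the SAP they are not.

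These patients are unlikely to be a random loss. Protocol 5.6.3 reports that withdrawals on MS1819 in OPTION were mainly due to increased symptoms of pancreatic insufficiency. What is at stake is whether the symptom experience of patients who stop MS1819 early for lack of effect appears anywhere in the efficacy output.

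**Working it through.** **Inputs**

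- Planned completers 30, withdrawal allowance 20%, planned enrolment 36 (Protocol 7.3.1).
- OPTION: 41 enrolled; 5 stopped during MS1819, 3 during PERT, and 1 after both periods (Protocol 5.6.3).
- The period in which the OPTION withdrawals occurred is not given.

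**The plan's own figure.** 30 × 1.20 = 36 reproduces the stated enrolment. Dividing instead, 30 / 0.80 = 37.5, or 38 after rounding up; the difference is immaterial here.

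**Membership, case by case**

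| Dosed patient | Protocol 7.3.4 | Synopsis, Protocol 10.3, SAP 4.1 |
|---|---|---|
| MS1819 first, leaves before completing the Visit 6 collection | in | out |
| PERT first, leaves before completing the Visit 6 collection | in only if the patient's own PERT counts as study product | out |
| Valid Visit 6 CFA, leaves in period 2 | in | in |

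The conflict is therefore confined to withdrawals without any valid CFA.

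**How many.** Let k be the number of such patients. With 36 enrolled and dosed, 7.3.4 gives up to 36 in the set and the other rule gives 36 − k.

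- All on-treatment withdrawals at the OPTION rate: 36 × 8/41 = 7.0.
- Of these, on MS1819: 36 × 5/41 = 4.4.
- Share in period 1: unknown, so it is taken from none to all. This gives k from 0 to about 7 overall (7/36 = 19.4%) and 0 to about 4 on MS1819 (4/36 = 11.1%).
- If half fell in period 1 (an assumption): 7.0/2 = 3.5 overall and 4.4/2 = 2.2 on MS1819.

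**Which outputs move**

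- *CFA, CNA, stool weight:* a value needs a collection, and SAP 9.1.1 states "Missing data will not be replaced". The same observed values are summarised under either rule.
- *Weight and BMI:* measured at Visits 1, 3, 6 and 9 (SAP 9.2.2.4) and not at the Early Withdrawal Visit. A patient gone before Visit 6 adds only baseline values.
- *Vitamins:* drawn at early withdrawal but summarised only at Visit 3, first dose and 3 weeks after first dose (SAP 9.2.2.5). Again essentially only baseline values are added.
- *Malabsorption symptoms:* assessed at Visits 3, 4 and 5 and at early withdrawal. SAP 9.2.2.3 summarises them at 1 and 2 weeks after first dose, so on-treatment values can exist well before any CFA. The stool-frequency summary, the shift tables and the listing are specified for mITT.
- *Adverse events:* Protocol 9.1.1 sends worsening EPI to a separate EPI form and does not count it as an AE unless it meets SAE criteria.
- *Counts and baseline tables:* SAP section 6 uses mITT, whereas Protocol 10.5 assigns these summaries to the Safety Set.

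Putting the last three together: a patient who stops MS1819 in period 1 for non-serious worsening of EPI has symptom data that reach no symptom table, no symptom listing and no AE table. What remains is mainly the withdrawal reason in the disposition output.

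**The case against.** The strongest reply is that the statistician has one rule. Three statements agree, 7.3.4 is the outlier in a section written for sites, and the SAP has primacy. That stands: there is no doubt about which set will be programmed. It does not remove the protocol's contradiction with itself, and it confirms that the symptom data of early leavers will be left out.

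A reader might infer more than the documents support:

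- *That the primary result, or every secondary table, depends on the rule chosen.* It does not. Neither rule creates a CFA for an unmeasured patient, and nothing is imputed. Any selection in the observed CFA mean is the same under both.
- *That the SAP hides the loss.* SAP 5.1 plans, for each dose and by sequence, the safety and mITT counts and the period 1 withdrawals with reasons. Safety N minus mITT N gives the number removed, and for a period 1 withdrawal the sequence identifies the treatment.
- *That SAP section 11 omits a change.* SAP 4.1 repeats Protocol 10.3, so on this definition there was nothing to declare.

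The scaling is also open to challenge. OPTION used immediate-release capsules at a single dose, and this crossover uses enteric capsules at two. The count is an indication only.

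**Conclusion.** The contradiction is real but narrow, covering only dosed patients who withdraw without a valid CFA. On OPTION rates this is 0 to about 7 of 36 patients, and 0 to about 4 if only those withdrawing on MS1819 are counted. The range rests on two assumptions: that OPTION withdrawal rates carry over, and that the unknown period 1 share lies anywhere from none to all.

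The primary CFA summary is unaffected, and no planned inferential conclusion depends on the point, because the analysis is descriptive and SAP section 11 drops the non-inferiority comparison. The material consequence is that the malabsorption-symptom output omits the patients most likely to show inadequate effect. That is worth correcting because the data are already collected and the correction is cheap.

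**What to change.** 1. Reconcile Protocol 7.3.4 with Protocol 10.3 and SAP 4.1 so that there is one mITT definition. The simplest route is to say in 7.3.4 that withdrawn, dosed patients enter the safety set, and enter the mITT set only if they meet the 10.3 condition.
2. Keep the CFA-evaluable set for CFA, CNA and stool weight.
3. Summarise and list malabsorption symptoms for all randomised, dosed patients by treatment received, using the values available.
4. Show n measured / N dosed by treatment in the CFA table.
5. Record the change of population for symptoms in SAP section 11, since Protocol 10.3 assigns all efficacy endpoints to mITT.

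The cost is a few lines of wording, a second population flag and one extra table row. Ns will differ slightly between the symptom and CFA tables, which a footnote can explain. CFA results do not change.

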### ***Pregnancy***

Patients will be instructed that known or suspected pregnancy occurring during the study, in patients or female partners of male patients, should be confirmed and reported to the Investigator. Any patient who becomes pregnant during the study must be promptly withdrawn from the study. Upon discontinuation from the study, only those procedures that would not expose the patient to undue risk will be performed. The Investigator should also be notified of pregnancy occurring during the study but confirmed after completion of the study. In the event that a patient is subsequently found to be pregnant after inclusion in the study, any pregnancy will be followed to term, and the status of mother and child will be reported to the Sponsor after delivery.

Full details will be recorded in the CRF, or an SAE report will be completed if the patient has completed the study.

## **7.4 Investigational Products Administered**

### **MS1819 Administration**

At the time of prescribing, the Investigator or delegated site staff will fill in a source document with the appropriate dosing instructions.

MS1819 doses will typically be fractionated as follows: 1/4 of the daily dosage at each of the 3 main meals, and 1/8 at each of the 2 snacks. For the 2240 mg/day dose, 2 capsules of

280 mg will be given with the morning, noontime, and evening meals, and 1 capsule of 280 mg will be given with the morning and evening snacks. For the 4480 mg/day dose, 4 capsules will be given with the three main meals, and 2 capsules given for the two snacks.

Please refer to [Table 2](#) for dosing guidance.

**Table 2: MS1819 Typical Dosing Schedule**

	Dose: 2240 mg/day	Dose: 4480 mg/day
Breakfast	2 x 280 mg capsules	4 x 280 mg capsules
Snack 1	1 x 280 mg capsule	2 x 280 mg capsule
Lunch	2 x 280 mg capsules	4 x 280 mg capsules
Snack 2	1 x 280 mg capsule	2 x 280 mg capsule
Dinner	2 x 280 mg capsules	4 x 280 mg capsules
Total	8 (280 mg) capsules/day	16 (280 mg) capsules/day

Note: Individual variations may occur as long as correct total daily dose is achieved.

### **Porcine PERT**

Patients will take their porcine PERT at the same dose that was being administered during the prestudy period, during the appropriate treatment period.

#### **7.4.3 Method of Assigning Patients to Treatment Groups (MS1819 2240 or 4480 mg)**

Patients will be randomized 1:1.

#### **7.5 Previous and Concomitant Therapy**

Standard-of-care medications are allowed (e.g., antibiotics, mucolytic agents, aerosols, CFTR modulators). Patients taking CFTR modulators should be on stable doses of the same modulator(s) for at least 3 months prior to screening. Patients should not start taking, or modify dose of, CFTR modulators for the duration of the study.

Gastric acid suppressants are allowed but must be on stable dosage of the same suppressant for 30 days before screening and must not be altered in dose or stopped during the study.

Prohibited medications during the entire clinical study will be as follows:

- Orlistat lipase inhibitor (e.g., Alli®, Xenical®)
- Laxatives consisting of mineral oil and castor oil; chronic use of osmotic laxatives is permitted
- Symptomatic treatments of diarrhea: loperamide (e.g., loperamide generic, Imodium®, Imodium A-D®, Diamode®, Imotil®, Kao-Paverin®); atropine/diphenoxylate (Lonox®); and atropine/diphenoxylate (Lomocot®).

## **7.6 Study Drug Materials and Management**

### **7.6.1 MS1819**

Study drug MS1819 will be supplied by the Sponsor for use in the protocol and is limited to investigational use only. Please refer to current Investigator's Brochure for additional information.

MS1819 is a 70% pure preparation of LIP2 protein. The concentrated ultra-filtration product obtained from fermentation is mixed with maltodextrin (1:2 ratio, based on the lipase dry weight) and subjected to spray drying (i.e., the drug substance). The drug product is formulated with inactive excipients and formulated in non-animal origin enteric capsules (Capsugel, Morristown, NJ, USA). MS1819 will be supplied as 280 mg, size zero capsules.

MS1819 will be provided in blister packs (wallets) in boxes and/or HDPE bottles

#### **7.6.1.1 MS1819 Shipment, Receipt, and Storage**

MS1819 will be supplied in blister packs and/or bottles to the sites by the Sponsor, in accordance with local requirements. The IMP will be shipped at room temperature. The site is responsible for the appropriate storage of the IMP. The IMP must be stored in a secured limited-access area and maintained at room temperature  $\leq 25^{\circ}\text{C}$ .

#### **7.6.1.2 MS1819 Misuse/Overdose**

Any IMP misuse or overdose associated or not associated with any AE should be reported to the Sponsor or designee as an SAE only if it meets the criteria of an SAE. Overdose is considered as dose taken above the prescribed daily dose for the current dosing phase.

### **7.6.1.3 MS1819 and porcine PERT Compliance**

The Investigator is responsible for ensuring compliance. Compliance with MS1819-SD will be cross-checked with study drug accountability and compliance with pre-study porcine PERT will be evaluated by subject self-report.

### **7.6.1.4 MS1819 Supply, Resupply, and Accountability**

On receipt, the pharmacist or delegated site staff will record the date, details of the bottle, and quantity of capsules.

The investigational sites will be re-supplied with IMPs according to their respective recruitment rates.

The pharmacist or delegated site staff will be provided with specific forms for accountability of the IMP (including the returned blisters and/bottles). Records will be kept up-to-date throughout the study and must be complete and accurate.

Used and unused IMPs must be made available to the Monitor or Sponsor designee who will verify the IMP accountability and cross-check pharmacy and Investigator records for compliance to the protocol requirements. Any discrepancy must be accounted for and documented.

### **7.6.1.5 MS1819 Return, Destruction, and Recall**

Return of IMP:

- Unused, partially used, empty blisters or bottles will be returned by the patient to the site at the end of each cycle.
- At the end of the study, the Sponsor will conduct a final reconciliation between delivered, dispensed, and used/unused IMPs.

Destruction of IMP:

- Unused, partially used, empty blisters or bottles must not be destroyed at the Investigative Sites without written authorization from the Sponsor.
- Unused, partially used, or empty blisters or bottles returned to the pharmacy will be destroyed at the Hospital Pharmacy or Sponsor's Drug Distributor only after IMP accountability forms have been fully and accurately completed and verified by the Monitor.

- If an on-site destruction is required, then the site must obtain written authorization for destruction from the Sponsor, which will be filed along with the certificate of destruction in the IMP section of the pharmacy site file.

Recall:

- If an IMP batch is suspected to be defective, then the Sponsor will immediately inform the Investigator and the hospital pharmacist.
- The Monitor will coordinate with the investigative site staff for the return of the concerned batches as per the return procedure. Depending on the study status, new batches may be sent to the investigational site.

